4.4.2.2 Overall Survival

OS is defined as the time from randomization to death from any cause. The analysis for OS will be conducted only in all randomized patients with detectable *PIK3CA*-mutant tumors as a secondary endpoint of the study and will be tested based on a hierarchical testing procedure to preserve type I error. That is, the OS will be tested only if both investigator-assessed PFS and ORR have reached their respective significance levels. The overall type I error for OS is preserved at two-sided 5%.

OS will be analyzed with patients grouped according to the treatment arm assigned at randomization. Data from patients who are alive at the time of the analysis data cutoff will be censored at the last date they are known to be alive. Data from patients without post-baseline information will be censored at the date of randomization.

The analyses will be conducted using the stratified two-sided log-rank test, and the results from the unstratified log-rank test will also be provided. The OS curve for each treatment arm will be estimated by the Kaplan-Meier method, and the HR and its 95% CI will be estimated by Cox proportional hazards models.

Three interim analyses (time driven) and one final analysis (event driven) for OS are planned in patients with detectable *PIK3CA*-mutant tumors (see [Table 2](#) and [Table 3](#)):

- The first interim OS analysis will be conducted at the time when both investigator-assessed PFS and ORR have reached their respective significance levels, so it could occur at the time of the interim efficacy or the final efficacy analysis for investigator-assessed PFS.
- The second interim analysis will be conducted approximately 10 months after the first interim analysis.
- The third interim analysis will be conducted approximately 8 months after the second interim analysis.
- The final analysis will be conducted after approximately 330 deaths are observed (approximately 77 months after FPI).

Table 2 Interim Analyses for Overall Survival if the First Interim Overall Survival Analysis Occurs at the Time of the Interim Efficacy Analysis of Investigator-Assessed Progression-Free Survival

	Estimated Timing (Clinical Data Cutoff)	OS Events	Two-Sided p-Value Boundary	Rejection HR Boundary ^a	Percentage Information
First OS IA	~21 months after FPI	~63	0.001	0.44	19%
Second OS IA	~10 months after first OS IA	~134	0.010	0.65	41%
Third OS IA	~8 months after second OS IA	~188	0.045	0.75	57%
OS FA	~77 months after FPI	~330	0.007	0.74	100%

FA=final analysis; FPI=first patient in; HR=hazard ratio; IA=interim analysis; OS=overall survival; PFS=progression-free survival.

^a Assuming exponential distributions for the OS event time of the two treatment arms.

Table 3 Interim Analyses for Overall Survival if the First Interim Overall Survival Analysis Occurs at the Time of the Final Efficacy Analysis of Investigator-Assessed Progression-Free Survival

	Estimated Timing (Clinical Data Cutoff)	OS Events	Two-Sided p-Value Boundary	Rejection HR Boundary ^a	Percentage Information
First OS IA	~29 months after FPI	~118	0.001	0.53	36%
Second OS IA	~10 months after first OS IA	~188	0.010	0.67	57%
Third OS IA	~8 months after second OS IA	~232	0.045	0.76	70%
OS FA	~77 months after FPI	~330	0.013	0.75	100%

FA=final analysis; FPI=first patient in; HR=hazard ratio; IA=interim analysis; OS=overall survival; PFS=progression-free survival.

^a Assuming exponential distributions for the OS event time of the two treatment arms.

The stopping boundaries are computed using the generalized Haybittle-Peto boundaries with unequal p-values being used in the α -spending function and will be adjusted on the basis of the actual number of OS events observed at each interim OS analysis.

The timing of the analyses are based on an assumption of an annual loss-to-follow-up rate of 5%. The study team will be unblinded at the time when the iDMC recommends to stop the study and the Sponsor decides to stop the study or at the time of the final PFS analysis if the study is not stopped early. Investigators and patients will remain blinded to individual patient-level treatment assignment until the final analysis of OS.

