3. STUDY DESIGN

3.1 DESCRIPTION OF STUDY

Study GO29058 (SANDPIPER) is a Phase III, randomized, multicenter, international, double-blind, placebo-controlled clinical study designed to compare the efficacy, as measured by PFS, and safety of fulvestrant+taselesib with that of fulvestrant+placebo after recurrence or progression following treatment with an AI for patients with ER+, HER2-negative, *PIK3CA*-mutant, unresectable, locally advanced or MBC. *PIK3CA* mutation status in all patients will be assessed by a central laboratory using the cobas® *PIK3CA* mutation test. In order to explore efficacy and differential benefit-risk in patients without a detectable *PIK3CA* mutation, 120 patients belonging to this category are planned for enrollment.

[figure not shown]
Study GO29058 will consist of a global study that will provide the evidence to determine the benefit-risk of taselesib plus fulvestrant in the target population; a possible extension cohort may continue to enroll only in China to meet local regulatory requirements.

In the global study, approximately 600 patients will be randomized in a 2:1 ratio to either fulvestrant+taselesib or fulvestrant+placebo (see [Figure 1](#)). unless the independent Data Monitoring Committee (iDMC) recommends stopping the study early and the Sponsor accepts the iDMC's recommendation. Patients whose tumors contain a *PIK3CA*-mutation (n=480) and patients whose tumors do not contain a detectable *PIK3CA*-mutation (n=120) will be randomized separately. After the global enrollment

closes, additional Chinese patients may continue to be recruited into the China extension cohort. A total of up to 150 Chinese patients with detectable PIK3CA-mutant tumors may be enrolled as part of the global study population and extension cohort combined (see Section 6.10). Patients enrolled as part of the China extension cohort will also be randomized in a 2:1 ratio to either fulvestrant+taselisib or fulvestrant+ placebo.

- **Taselisib Arm:** Taselisib 4-mg tablet dose (2×2 mg tablet formulation) taken orally (PO) QD beginning at Cycle 1, Day 1 and fulvestrant 500 mg administered by IM injection at Cycle 1, Days 1 and 15, and then on Day 1 of each subsequent 28-day cycle
- **Control Arm:** Placebo taken PO QD beginning at Cycle 1, Day 1 and fulvestrant 500 mg administered by IM injection at Cycle 1, Days 1 and 15, and then on Day 1 of each subsequent 28-day cycle

Figure 1 Schematic of Randomized Controlled Study GO29058 (Global Study)

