Table 2	Interim Analyses for Overall Survival if the First Interim Overall Survival Analysis Occurs at the Time of the Interim Efficacy Analysis of Investigator-Assessed Progression-Free Survival	13
Table 3	Interim Analyses for Overall Survival if the First Interim Overall Survival Analysis Occurs at the Time of the Final Efficacy Analysis of Investigator-Assessed Progression-Free Survival	14

LIST OF APPENDICES

Appendix 1	Protocol Synopsis	23
Appendix 2	Schedule of Assessments.....	33

1. **BACKGROUND**

Study GO29058 is a Phase III, double-blind, multicenter, randomized, placebo-controlled study designed to evaluate the efficacy and safety of taselisib + fulvestrant compared with placebo + fulvestrant in postmenopausal women with estrogen receptor-positive and human epidermal growth factor 2 (HER2)-negative locally advanced or metastatic breast cancer (MBC) who have disease recurrence or disease progression during or after aromatase inhibitor therapy.

Approximately 600 patients will be enrolled in the global study, including 480 patients with detectable *PIK3CA*-mutant tumors and 120 patients without detectable *PIK3CA*-mutant tumors. Patients will be randomized in a 2:1 ratio to receive either fulvestrant + taselisib or fulvestrant + placebo. Patients with and without detectable *PIK3CA*-mutant tumors will be randomized separately.

The primary efficacy endpoint is investigator-assessed progression-free survival (PFS) in patients with detectable *PIK3CA*-mutant tumors, and the secondary efficacy endpoints are overall objective response rate (ORR), overall survival (OS), clinical benefit rate (CBR), duration of objective response (DOR), and blinded independent central review (BICR)-assessed PFS in patients with detectable *PIK3CA*-mutant tumors. The safety of taselisib and fulvestrant compared with placebo and fulvestrant will be evaluated in patients with detectable *PIK3CA*-mutant tumors and also in all randomized patients who receive at least one dose of any component of protocol treatment (i.e., study drug).

The purpose of this Statistical Analysis Plan (SAP) is to provide the analysis plan proposed for this study by the Sponsor, F. Hoffmann-La Roche Ltd. The SAP overrides the analyses described in the statistical section of the protocol. The analyses as described in the SAP will be used by the Sponsor for the purpose of regulatory submission.

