2.3 DETERMINATION OF SAMPLE SIZE

The global study plans to enroll approximately 600 patients, including 480 patients with detectable *PIK3CA*-mutant tumors and 120 patients without detectable *PIK3CA*-mutant tumors (tumor status determined by the cobas[®] *PIK3CA* Mutation Test).

After the global enrollment closes, additional Chinese patients may continue to be recruited into the China extension cohort. A total of up to 150 patients with detectable *PIK3CA*-mutant tumors may be enrolled as part of the global study population and the China extension cohort combined (refer to the protocol for details).

The sample size of 480 patients with detectable *PIK3CA*-mutant tumors is determined on the basis of the power calculation for the PFS and the OS endpoints, whichever requires a larger sample size. In this case, the sample size is driven by OS.

Among the 480 patients with *PIK3CA*-mutant tumors, approximately 287 investigator-assessed PFS events will be required to detect a hazard ratio (HR) of 0.59 in PFS (3.1 months of improvement in median PFS) with 95% power at a two-sided significance level of 1%, assuming a median PFS of 4.5 months in the control arm ([Mauriac et al. 2009](#); [Johnston et al. 2013](#)). One interim efficacy analysis of investigator-assessed PFS will be conducted at 60% of PFS information (see [Section 4.8](#) for more details). The α -spending function is specified as Gamma ($\alpha = 16$), which allocates two-sided $\alpha = 1.7 \cdot 10^{-5}$ at the interim efficacy analysis of PFS, when 172 investigator-assessed PFS events have occurred. The minimal detectable difference for PFS HR at final PFS analysis is 0.72 (i.e., 39% improvement in median PFS from 4.5 months in the control arm compared with 6.2 months in the treatment arm), when 287 investigator-assessed PFS events have occurred.

With the aforementioned sample size of 480 patients with *PIK3CA*-mutant tumors, the OS analyses in this population will require 330 deaths to detect an HR of 0.7 with at least 80% power at a two-sided significance level of 5%. Timeline for the analyses of OS is detailed in [Section 2.4](#). OS will be tested only if both the investigator-assessed PFS and ORR have reached their respective significance levels.

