4.8 INTERIM ANALYSES

The iDMC will convene to review cumulative safety data approximately every 6 months. Data on serious adverse events, death, and adverse events of special interest will be monitored by the iDMC approximately every 3 months.

One efficacy and futility analysis for investigator-assessed PFS will be conducted in patients with detectable *PIK3CA*-mutant tumors when approximately 172 investigator-assessed PFS events (approximately 60% of the information, expected at approximately 23 months after FPI) have occurred in patients with *PIK3CA*-mutant tumors. Approximately 320 patients with detectable *PIK3CA*-mutant tumors and approximately 120 patients without detectable *PIK3CA*-mutant tumors will have been randomized into the study by the time of the interim analysis. The actual timing of the interim analysis and the number of patients randomized will depend on the accrual rate and actual accumulation of PFS events observed in the study.

The iDMC will review the efficacy while the Sponsor and investigators remain blinded to the treatment assignment.

The iDMC may recommend stopping the study for efficacy at the interim efficacy analysis of investigator-assessed PFS, when the two-sided p-value $\leq 1.7 \cdot 10^{-5}$, with approximately 172 investigator-assessed PFS events at the interim efficacy analysis. The α -spending function is specified as Gamma ($\alpha = 16$), which allocates two-sided $\alpha = 1.7 \cdot 10^{-5}$ at the interim efficacy analysis when approximately 172 PFS events are reached and preserves the two-sided 1% α -level at the final PFS analysis. The actual boundary will be adjusted based on the actual number of investigator-assessed PFS events at the interim analysis. If the iDMC recommends stopping the study for efficacy at the interim analysis and the Sponsor decides to stop the study, the study team will be

unblinded, and the investigators and patients will remain blinded to individual patient-level treatment assignment until the final OS analysis.

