In 480 patients with *PIK3CA*-mutant tumors, approximately 287 investigator-assessed PFS events will be required to detect a hazard ratio of 0.59 in PFS (3.1 months of improvement in median PFS) with 95% power at the a two-sided significance level of 1%, assuming a median PFS of 4.5 months in the control arm (Mauriac et al. 2009; Johnston et al. 2013). *One interim efficacy analysis of investigator-assessed PFS will be conducted at 60% of PFS. The α -spending function specified as Gamma (-16), which allocates two-sided $\alpha = 1.7 \cdot 10^{-5}$ at the interim efficacy analysis of investigator-assessed PFS, when 172 investigator-assessed PFS events have occurred. The minimal detectable difference for investigator-assessed PFS hazard ratio at final PFS analysis is 0.72 (i.e., 39% improvement in median investigator-assessed PFS from 4.5 months in the control arm compared with 6.2 months in the treatment arm), when 287 investigator-assessed PFS events have occurred.*

With the aforementioned sample size of 480 patients with *PIK3CA*-mutant tumors, the OS analyses in this population will require 330 deaths to detect an hazard ratio of 0.7 in OS (11.1 months of improvement in median OS) with 80% power at a two-sided significance level of 5%, assuming a median OS of 26 months in the control arm based on the OS of 26.4 months in patients treated with 500 mg fulvestrant in the CONFIRM study, which investigated 500 mg fulvestrant versus 250 mg fulvestrant in a similar patient population (Di Leo et al. 2014).

The study plans to enroll 120 patients who do not have a detectable *PIK3CA*-mutant tumor, on the basis of the result of the cobas *PIK3CA* mutation test, to evaluate the clinical benefit in this population. If the observed hazard ratio in *investigator-assessed* PFS is 1 (no benefit), approximately 111 *investigator-assessed* PFS events will be observed at the analysis, and the 90% confidence interval will exclude a true hazard ratio < 0.72 (i.e., > 1.8 -month improvement in median PFS).

In total, approximately 400 patients will be treated with the combination of taselelisib + fulvestrant in this study (320 patients with *PIK3CA*-mutant tumors and 80 patients without detectable *PIK3CA*-mutant tumors), which will enable the Sponsor to better characterize any rare but clinically significant safety events (e.g., for an adverse event with 4% frequency, there is 96% probability to observe $\alpha = 10$ patients with such adverse event on the basis of

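### SAP Table 2 assumes mutant-cohort accrual to 480; if the Sponsor stops for efficacy at the PFS interim with about 320 patients, its 330-death final OS analysis is out of reach, and even at 480 its boundaries give about 74% power

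*Combined protocol and SAP*

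**What the plan says.** SAP 4.4.2.2 gives two OS schedules. Table 2 applies if the first OS interim falls at the PFS interim, about 21 months after the first patient in (FPI). It plans 63, 134, 188 and 330 deaths with two-sided p-value boundaries 0.001, 0.010, 0.045 and 0.007. Table 3 applies if the first OS look falls at the final PFS analysis, about month 29. It plans 118, 188, 232 and 330 deaths with boundaries 0.001, 0.010, 0.045 and 0.013. Both end the same way: "The final analysis will be conducted after approximately 330 deaths are observed (approximately 77 months after FPI").

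On power, SAP 2.3 says that in 480 mutant patients the OS analyses "will require 330 deaths to detect an HR of 0.7 with at least 80% power at a two-sided significance level of 5"%.

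On accrual, SAP 4.8 says "Approximately 320 patients with detectable" PIK3CA-mutant tumours will have been randomised by the PFS interim. Protocol 3.1, and the synopsis reproduced in SAP Appendix 1, plan about 600 patients (480 mutant) unless the iDMC "recommends stopping the study early and the Sponsor accepts" that recommendation. Protocol 9.4 attaches the same proviso to enrolment explicitly.

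OS follow-up is meant to outlive an efficacy stop. SAP 4.8 says that in that event "the investigators and patients will remain blinded to individual patient-level treatment assignment until the final OS analysis".

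**The concern.** The proviso implies that if the Sponsor accepts a recommendation to stop for efficacy, mutant accrual ends near 320. Table 2 is the OS schedule that would then be in force, and it asks for 330 deaths, which is 330/320 = 103% of those patients. No passage says that accrual continues after an efficacy crossing, and none gives an OS event target for a smaller cohort.

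Table 2's own counts show which population it was built on. Its third look is at 21 + 10 + 8 = month 39 with about 188 deaths. Table 3's second look is at 29 + 10 = month 39, also with about 188 deaths. Those agree only if both assume the same accrual, to 480.

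At stake in an efficacy stop are the final event target, the information fractions (19/41/57/100%), the boundaries and the power.

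**Working it through.** **Inputs.** From the documents: control median OS 26 months and HR 0.7 (Protocol 6.1; SAP Appendix 1: "assuming a median OS of 26 months in the control arm"); 5% annual loss to follow-up (SAP 4.4.2.2); 2:1 allocation (SAP Section 1); 12-month site ramp-up and 480 mutant patients by month 28 (SAP 2.4). Assumed: a linear ramp to a constant rate, and exponential survival and loss.

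**Accrual.** Rate R = 480/(12/2 + 16) = 21.8 per month after the ramp. At month 21 this gives R × (6 + 9) = 327 patients, close to the stated 320.

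**Deaths.** For a patient entering at u with death hazard λ and loss hazard γ, the probability of an observed death by month t is λ/(λ+γ) × [1 − exp(−(λ+γ)(t−u))]. Here λ(control) = ln 2/26 = 0.02666, λ(taselisib) = HR × 0.02666, and γ = −ln(0.95)/12 = 0.00427. Arms are weighted 1/3 and 2/3.

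**Reproducing the plan.** With accrual to 480, the model (HR 0.7 to HR 1) gives 118–142 deaths at month 31 (Table 2: 134), 169–201 at month 39 (188) and 310–348 at month 77 (330). Table 2's later counts therefore fit 480 patients. Its month-21 count of 63 is slightly above the model's 48–59.

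**Accrual ended early.** Ranges run from HR 0.7 to HR 1.

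| Accrual ends | Patients | Deaths, month 77 | Ceiling |
|---|---|---|---|
| Month 21, scaled to 320 | 320 | 212–237 | 266–276 |
| Month 21 | 327 | 217–243 | 272–282 |
| Month 23 | 371 | 244–273 | 308–320 |
| Month 24 | 393 | 258–289 | 326–338 |
| Month 25 | 415 | 271–304 | 344–357 |

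The ceiling is the head count times the chance that death precedes loss. At HR 0.7 that chance is (2/3) × 0.8136 + (1/3) × 0.8618 = 0.830; at HR 1 it is 0.862. So 320 × 0.830 = 266 and 327 × 0.862 = 282. Observing 330 deaths at all needs about 330/0.862 = 383 to 330/0.830 = 398 patients. With accrual ended at month 21 the earlier looks shrink too: 96–118 deaths at month 31 and 127–154 at month 39.

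**Power at HR 0.7.** The log-rank Z at d deaths has mean √(d × 2/9) × 0.3567.

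- Single look, two-sided 5%: 80% power needs (1.960 + 0.842)²/[(2/9) × 0.3567²] = 278 deaths; 330 deaths give 86.3%.
- Table 3's four looks, simulated at 2:1: 79.3%. This reproduces the stated 80% to within a point.
- Table 2's four looks (63/134/188/330), simulated at 2:1: 74.0%.
- Table 2's p-values at the reduced counts (48/96/127/212): 54%.

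Simulated two-sided type I error is about 5.0% for both tables. A possible source of the Table 2 shortfall is that three of its four HR boundaries (0.44, 0.75, 0.74) match 1:1 allocation (0.436, 0.746, 0.743) rather than 2:1 (0.415, 0.733, 0.730). At 1:1 the same looks give about 79%.

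**The case against.** The strongest reply is that Table 2 is triggered by statistical significance of PFS and ORR, not by stopping. The iDMC only may recommend stopping, and the Sponsor must then agree. If it does not, accrual runs to 480 and Table 2 is attainable. The documents also do not define a stop as closing accrual. This stands: a reader might infer that 330 deaths can never be reached in the Table 2 branch, and the text does not support that. It supports only the conditional statement about an accepted efficacy stop.

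Second, 320 is approximate and counts patients at the interim, not at the decision. SAP 4.8 times the interim at about month 23, where other sections say 21. Accrual to month 23 still leaves a ceiling of 308–320, but a lag to month 24 or 25 could make 330 reachable in the end. That also stands, though month-77 deaths would still be at most about 304.

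Third, month-77 deaths should not be judged against 330 alone, since the same model gives only about 310 at HR 0.7 with full accrual. That is fair. The ceiling is the firmer comparison.

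Fourth, the branch was unlikely: crossing 1.7 × 10⁻⁵ at 172 events has probability about 15% at HR 0.59 and about 2% at HR 0.70. It was also not taken. The protocol amendment summary reports the primary PFS analysis in January 2018 with p = 0.0037, which could not have crossed that boundary. Protocol Version 4 has dropped the third interim and final OS analyses, so its Table 12 has no 330-death row. All true. But SAP Section 1 says the SAP overrides the protocol's statistical section, and SAP Version 2 still carries all four looks.

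**Conclusion.** The SAP holds two incompatible assumptions about accrual after an efficacy stop. Table 2 needs 480 mutant patients, while the early-stopping proviso implies about 320. If accrual ended at month 21, about 212–243 deaths are expected by month 77 and at most about 266–282 ever, so the planned final OS analysis could not take place. Power at HR 0.7 with Table 2's p-values would be about 54%. A somewhat higher figure might be inferred from the larger death counts, but those arise under HR 1 and cannot be paired with power at HR 0.7. These figures rest on the planning values, the assumed linear ramp and little decision lag.

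A second defect does not depend on stopping. With 480 patients and 330 deaths, Table 2's boundaries at 2:1 give about 74% power, not "at least 80% power at a two-sided significance level of 5"%. Table 3 gives about 79%.

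A reader might also infer that type I error is inflated or that the reported results are affected. Neither follows: simulated type I error is about 5%, and the Table 2 branch was not taken. The practical effect is limited to the coherence of the documented design.

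**What to change.** In SAP 4.8 and 4.4.2.2, do one of two things. Either state that mutant-cohort enrolment continues to 480 after an efficacy crossing, and restate OS power for the Table 2 branch as about 74%. Or re-derive Table 2's event counts, information fractions, boundaries and power for about 320 patients.

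In the protocol, only the remaining second-look row of Table 12 (134 deaths, 41%) is affected. It needs the same accrual statement, or a count consistent with accrual ending at the interim (about 96–118 deaths, which is 29–36% of 330).

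The cost is a few sentences and one recalculation. The stated OS power for this branch becomes less favourable.
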